7.4. Inclusion criteria

Patients must satisfy all the following entry criteria before they are allowed to participate in the study.

TUMOR CHARACTERISTICS:

- Histologically or cytologically confirmed diagnosis of rhabdomyosarcoma (new biopsy recommended)
- Any Relapsed / progressive disease (in patients who have already presented a response to chemotherapy)

OR

- Refractory disease (defined as progression after receiving chemotherapy without prior response)
- Patients must have measurable disease defined as lesions that can be measured in 3 dimensions by medical imaging techniques such as CT or MRI. Ascites, pleural fluid, bone marrow disease alone and lesions seen on Tc scintigraphy or PET scan only are not considered measurable.

PATIENT CHARACTERISTICS:

- Age > 6 months and ≤ 50 years
- Karnofsky performance status (PS) 70-100% (for patients > 12 years of age)
OR Lansky Play Score 70-100 % (for patients ≤ 12 years of age)
- Life expectancy ≥ 12 weeks
- Adequate bone marrow function :
 - Absolute neutrophil count ≥ 1000/mm³
 - Platelet count ≥ 100,000/mm³ (transfusion independent)
 - Hemoglobin ≥ 8.5 g/dL (transfusion allowed)

- In case of bone marrow disease:
 - Absolute neutrophil count $\geq 500/\text{mm}^3$
 - Platelet count $\geq 75,000/\text{mm}^3$
- Adequate renal function
 - Serum creatinine $\leq 1.5 \times \text{ULN}$ for age
 - If serum creatinine $> 1.5 \text{ ULN}$, creatinine clearance (or radioisotope GFR) must be $\geq 70 \text{ ml/min/1.73 m}^2$
- Adequate hepatic function :
 - Total bilirubin ≤ 1.5 times upper limit of normal (ULN) for age, except if the patient is known to have Gilbert's syndrome
 - ALT and AST $\leq 2.5 \times \text{ULN}$ for age
- Negative pregnancy test in females with childbearing potential
- Fertile patients must use effective contraception
- No active $>$ grade 2 diarrhea or uncontrolled infection
- No other malignancy, including secondary malignancy
- Patient affiliated with a health insurance system. Applicable for French patients only
- Written informed consent of patient and/or parents/ guardians

PRIOR OR CONCURRENT THERAPY:

- More than 3 weeks since prior radiation therapy to the site of any progressive lesion that will be identified as a target lesion to measure tumor response
- At least 3 weeks since prior myelosuppressive therapy (6 weeks for nitrosourea, 2 weeks for vincristine, vinorelbine, vinblastine and low-dose cyclophosphamide)

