11. OUTCOME MEASUREMENTS

11.1. Efficacy and treatment administration endpoints

11.1.1. Objective tumour response and progression

Measurements of all lesions should be recorded in metric units. All baseline evaluations should be performed as closely as possible to the treatment start, within 14 days of the beginning of the treatment if possible. The same radiological modality and technique (same sequence) for assessing disease at study entry is to be used for reassessment so that a direct comparison can be made to accurately evaluate disease response.

This study will use volumetric measurements of the primary tumour using an elliptical model (0.52 times the product of the 3 largest perpendicular diameters in the axial, coronal and sagittal plane) to assess response to neo adjuvant therapy. The RECIST 1.1 (Response Evaluation Criteria in Solid Tumours; *ref New response evaluation criteria in solid tumours: Revised RECIST guideline (version 1.1) European Journal of Cancer 45 (2009) 228–247*) criteria will be used for assessment of the size of measurable metastases, including nodal metastases (see Section 10.1.3.).

Primary Tumour Response (Volumetric)

On the basis of previous reports showing that volumetric tumour measurements may be more accurate than bidirectional or unidirectional measurements for tumours measuring $>35 \text{ cm}^3$, we will obtain volumetric measurements of the primary tumour using the formula for an ellipsoid model: volume 0.52 (antero-posterior diameter x transverse diameter x length) [Sohaib 2000, Prasad 2002].

Tumour volume (V) calculation:

a = length (in cm)

b = width (in cm)

c = thickness (in cm)

$$V = \pi/6 \times a \times b \times c = 0.52 \times a \times b \times c \text{ in cm}^3$$

It is planned to also measure the maximum uni-dimensional measurement as suggested by the RECIST 1.1 guidelines (*European Journal of Cancer 2009; 45: 228-47*) and later compare the volume with uni-dimensional measurements in terms of tumour response. The maximum lesion diameter in any plane should be recorded as the longest tumour diameter and measurements may be taken from CT or MRI, but the maximum tumour measurement must always be in the same plane (axial, coronal or sagittal) even if this results in measuring the lesion at a different slice level or in a different orientation or vector compared with the baseline study.

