A clinical assessment should be done at each visit in order to detect tumour progression at any point during treatment. This should be supplemented by radiological examination as appropriate.

RELATIONSHIP BETWEEN CHANGE IN SINGLE DIAMETER (RECIST), PRODUCT OF TWO DIAMETERS (WHO), AND THREE PERPENDICULAR DIAMETERS ("VOLUME")

	Diameter, 2R	Product,(2R) ²	Volume, 4/3πR ³
Response	Decrease	Decrease	Decrease
	13%	24%	33%
	30%	50%	65%
	50%	75%	87%
Disease Progression	Increase	Increase	Increase
	12%	25%	40%
	20%	44%	73%
	25%	56%	95%
	30%	69%	120%

Response evaluation criteria (Volumetric)

Complete Response (CR)	Complete disappearance of all visible disease
Partial Response (PR>2/3)	≥ 65% reduction of tumour volume (volume response between 65-99%)
Minor Partial Response (PR<2/3)	Volume response between 34-64%
Stable Disease (SD)	No criteria for PR or PD
Progressive Disease (PD)	Any increase of more than 73% of any one target lesion/tumour volume or appearance of new lesions.

All responses must last at least 4 to 5 weeks without evidence of tumour progression or relapse.

Metastatic Disease Measurement

The RECIST 1.1 (*European Journal of Cancer 2009; 45: 228–47*) criteria will be used for assessment of the size of measurable metastases, including nodal metastases.

RECIST Methodology

Planes and techniques:

- CT: The same method of assessment and the same technique should be used to characterize each identified and reported lesion at baseline and during follow-up. Lesions should be measured on the same window setting on each examination.
- MRI: Lesions must be measured in the same anatomic plane by use of the same imaging sequences on subsequent examinations.

Measurements:

DIAGNOSIS

- **Measurable lesion:** A lesion that can be accurately measured in at least 1 dimension with the longest diameter at least twice the thickness of the CT or MR slice with a minimum of 10 mm (for lymph nodes ≥15 mm shortest axis). This is defined as a "**target lesion**". The investigator will identify up to 5 target lesions total and up to 2 per organ to be followed for response. In general, the largest lesions representative of involved organs are selected to follow as target lesions. However, in some cases, the largest lesions may not be easily measured and are not suitable for follow-up because of their configuration. In these cases, identification of the largest most reproducible lesions is advised. Serial measurements of

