target lesions are to be done with CT or MRI. The sum of the longest diameters of all target lesions will be calculated and reported as the measurable metastatic disease measurement.

Non target: All other lesions (or sites of disease) including pathological lymph nodes should be identified as non-target lesions and should also be recorded at baseline and follow up.

- **Non-measurable:** All lesions that do not qualify as target lesions (all lesions whose largest diameter is less than twice the thickness of the CT or MRI slice, and all truly non-measurable disease such as bone lesions*, leptomeningeal disease, ascites, pleural/ pericardial effusions, lymphangitis cutis/pulmonis, and cystic lesions**).

Special note on lymph nodes:

Pathological nodes which are defined as measurable and may be identified as target lesions must meet the criterion of a short axis of ≥ 15 mm. Only the short axis of these nodes will contribute to the baseline sum. All other pathological nodes (those with short axis ≥ 10 mm but < 15 mm) should be considered non-target lesions. Nodes that have a short axis < 10 mm are considered non-pathological and should not be recorded or followed.

**Special note on bone lesions:*

Lytic bone lesions or mixed lytic-blastic lesions, with identifiable soft tissue components, that can be evaluated by cross sectional imaging techniques such as CT or MRI can be considered as measurable lesions if the soft tissue component meets the definition of measurability described above. All other bone lesions are considered non-measurable.

***Special note on cystic lesions:*

'Cystic lesions' thought to represent cystic metastases can be considered as measurable lesions, if they meet the definition of measurability described above. However, if non-cystic lesions are present in the same patient, these are preferred for selection as target lesions.

FOLLOW UP

- The same method of assessment is to be used to characterize each identified and reported lesion at baseline and during follow-up. Using the same plane of evaluation, the maximal diameter of each target lesion should always be measured at subsequent follow-up time points even if this results in measuring the lesion at a different slice level or in a different orientation or vector compared with the baseline study.

Metastatic Tumour Response

Target Lesions (RECIST):

- Complete Response (CR): Disappearance of all target lesions.

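### Entry and response scoring define measurable disease differently, so a patient with only small metastatic or nodal lesions can enter yet never be scored a partial response

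*Protocol*

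**What the plan says.** **Entry (section 7.4).** "Patients must have measurable disease defined as lesions that can be measured in 3 dimensions by medical imaging techniques such as CT or MRI". The exclusions that follow are by type, not size: "Ascites, pleural fluid, bone marrow disease alone and lesions seen on Tc scintigraphy or PET scan only are not considered measurable".

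**Primary-site scoring (section 11.1.1).** "we will obtain volumetric measurements of the primary tumour using the formula for an ellipsoid model". PR is "≥ 65% reduction of tumour volume (volume response between 65-99" per cent), with no lower limit on baseline size.

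**Metastatic scoring (section 11.1.1).** The RECIST 1.1 "criteria will be used for assessment of the size of measurable metastases, including nodal metastases". Under this system a measurable lesion, which the section calls a target lesion, may be measurable in one dimension only, but it must span at least two slice thicknesses and reach a size floor, stated as "minimum of 10 mm (for lymph nodes ≥15 mm shortest axis"). Lesions that do not qualify as targets are called non-measurable. For nodes: "All other pathological nodes (those with short axis ≥ 10 mm but < 15 mm) should be considered non-target lesions".

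**Response classes (section 11.1.1).** Metastatic PR is a fall of at least 30% in the summed diameters of target lesions. Non-target lesions have three classes: CR, SD and PD.

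**Endpoint and analysis set.** The primary endpoint (section 11.1.3) is confirmed CR or PR after two cycles. The main analysis (section 12.2) is by intent to treat in all included patients. The revised rule in section 12.1 calls VIT sufficiently active if at least 22 of 47 evaluable VIT patients respond.

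**The concern.** The protocol uses one word with two meanings. Section 7.4 asks for three dimensions and no minimum size. Section 11.1.1 asks, for metastases, for one dimension and a minimum size. A patient whose only disease is, say, 8 mm lung nodules or a 12 mm short-axis node can satisfy the first and fail the second. That patient is eligible as having measurable disease and is then scored as having none.

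The primary endpoint counts CR and PR, and such a patient has no route to PR. The patient is nevertheless in the denominator of the rate that is held against a fixed cut-off. The response rate then partly reflects how many patients with small-volume metastatic or nodal disease were admitted, as well as the activity of the treatment.

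**Working it through.** **1. Follow one patient through the text.** Assume only metastatic or nodal lesions, all below the floor.

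| Step | Section | Result |
|---|---|---|
| Three diameters can be taken on CT or MRI | 7.4 | Eligible |
| Below 10 mm or twice slice thickness; node below 15 mm short axis | 11.1.1 | Not a target lesion |
| PR needs a 30% fall in the target-lesion sum | 11.1.1 | Not available |
| Non-target classes | 11.1.1 | CR, SD or PD |
| Overall-response table | 11.1.2 | No row reaches PR from non-target disease alone |
| Analysis set | 12.2 | All included patients, so in the denominator |

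The evaluable definition in section 12.2 (two cycles given, tumour evaluation at two cycles available) does not remove this patient. Nor does the eligibility condition of the per-protocol set, because section 7.4 was met.

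**2. Check that primary-site lesions escape.** A 9 mm spherical lesion has volume 0.52 × 0.9³ = 0.38 cm³. A 65% reduction leaves 35% of the volume, a diameter of 9 × 0.35^(1/3) = 6.3 mm. Nothing in the volumetric criteria stops this being scored PR. The gap is confined to metastatic and nodal disease.

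**3. Reproduce the plan's rule.** Inputs from section 12.1: n = 47, cut-off 22, p0 = 0.35, p1 = 0.55, both error rates 0.10. Exact binomial:

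- P(X ≥ 22 | 47, 0.35) = 0.063, below the 0.10 ceiling.
- P(X ≥ 22 | 47, 0.55) = 0.899, against the stated 0.90.

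The rule is correct as stated.

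**4. Size the consequence.** The protocol does not give the number k of affected patients, so k = 2 and k = 5 are assumptions (2/47 = 4.3%, 5/47 = 10.6%). Suppose the other 47 − k respond at 0.55 and the affected k never respond. Power is then P(Bin(47 − k, 0.55) ≥ 22):

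- k = 2: P(Bin(45, 0.55) ≥ 22) = 0.835.
- k = 5: P(Bin(42, 0.55) ≥ 22) = 0.691.

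**5. Let CR back in.** If the affected patients reach CR with probability q, power is P(Bin(47 − k, 0.55) + Bin(k, q) ≥ 22). With q assumed at 0.20 and 0.40:

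| k | q = 0 | q = 0.20 | q = 0.40 | q = 0.55 |
|---|---|---|---|---|
| 2 | 0.835 | 0.860 | 0.882 | 0.899 |
| 5 | 0.691 | 0.782 | 0.855 | 0.899 |

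At q = 0.55 nothing is lost, and above it power would rise. The sign of the effect therefore depends on a quantity that the documents do not give.

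**The case against.** **Such patients can still respond.** This stands. Non-target CR is defined and counts towards the endpoint. Section 11.1.1 also treats nodes under 10 mm short axis as non-pathological. On that reading a 12 mm node needs to shrink by only just over 2 mm to count as gone, which may be easier than a 30% fall. A reader might infer that these patients are certain non-responders and that the rate is biased downwards. The text supports neither; it supports only that PR is closed to them.

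**Few patients may be affected.** This stands as far as the documents go. Section 5.1 gives isolated metastatic recurrence as 15% of relapses after localised disease. On that figure alone, the assumed 2 to 5 of 47 would need 4.3/15 = 28% to 10.6/15 = 71% of such relapses to consist only of sub-threshold lesions. Nodal locoregional disease could add some, but no number is given.

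**The entry text presupposes a target lesion.** Other bullets of section 7.4 mention a target lesion when dealing with radiotherapy. This makes enrolment without one less likely, but those bullets set no minimum size and do not require a target lesion.

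**Accrual may be complete.** The version 5.1 change log already discusses the effect of VIT on survival, which suggests that enrolment is over or nearly so. Rewording section 7.4 would then change little. Classifying patients already entered would still matter.

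**Stronger readings that fail.** A reader might infer that no lesion under 10 mm can be scored PR; step 2 of the working shows that this is wrong for primary-site lesions. A reader might also take the 35 cm³ mentioned in section 11.1.1 as a limit below which volumetry is invalid. The text offers it as a reason for preferring volume in larger tumours, not as a limit.

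**Conclusion.** The two definitions conflict, and the conflict reaches the primary endpoint by a specific route: sub-threshold metastatic or nodal disease is measurable for entry, non-target for scoring and closed to PR, while the patient stays in the denominator. Primary-site lesions are outside the problem, and no stated figure in the sample-size section is wrong on this account.

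The size is unknown. Under the assumption that 2 to 5 of 47 VIT patients are affected and none responds, power falls from 0.90 to 0.84–0.69. This is the worst case for those counts, not an estimate. Any CR among them shrinks the loss, and a CR rate above 0.55 would reverse it. The supported conclusion is that the response rate has an avoidable ambiguity of uncertain direction, not that it is biased by a known amount.

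**What to change.** 1. Reconcile sections 7.4 and 11.1.1 so that entry requires at least one lesion scorable for PR: either a primary-site lesion measurable in three dimensions, or a metastatic or nodal lesion that meets the target-lesion definition of section 11.1.1. State whether the three-dimension requirement still applies to the metastatic route, since the target-lesion definition asks for only one.
2. For patients already entered, have the blinded central review (section 13.9) record from the baseline images whether such a lesion was present.
3. Report the response rate in each arm with and without patients who had none. The intent-to-treat result stays the main one; the second shows how much the gap matters.

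The cost is a short change to the entry criterion and one field on the review form. Baseline images are already collected. If enrolment is still open, a few patients with very small metastatic or nodal relapse would no longer qualify. If it is closed, items 2 and 3 carry the value.

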- No concurrent enzyme-inducing anticonvulsants (EIA), including phenytoin, phenobarbital, or carbamazepine
- No concurrent administration of any of the following : rifampicin, voriconazole, itraconazole, ketoconazole, aprepitant
- No prior irinotecan or temozolomide administration
- Prior administration of vincristine is allowed
- Concurrent palliative radiation therapy to sites allowed except for the main measurable target lesion
- Prior allo- or autologous SCT allowed

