9. TREATMENT ADMINISTRATION

9.1. Starting doses and schedules

ARM A		
D1 and D8 Vincristine	1.5 mg/m ² /d – IV bolus (0.05 mg/kg for patient ≤ 10 kg)	3 weekly
D1 to D5 Irinotecan	50 mg/m ² /d – IV over 1 hour	3 weekly
ARM B		
D1 to D5 Temozolomide	125 mg/m ² /d - PO	3 weekly
D1 and D8 Vincristine	1.5 mg/m ² /d – IV bolus (0.05 mg/kg for patient ≤ 10 kg)	3 weekly
D1 to D5 Irinotecan	50 mg/m ² /d – IV over 1 hour	3 weekly

Vincristine: The dose of vincristine will be 1.5 mg/m² or 0.05 mg/kg for patient ≤ 10 kg (maximum 2.0 mg) and will be administered by direct intravenous infusion on day 1 and day 8 of each course, before irinotecan. Administration must comply with guidance on administration of vinca alkaloids as per NPSA/2008/RRR004.

Irinotecan: The dose of irinotecan will be 50 mg/m²/day. Irinotecan will be given intravenously infusion over 1 hour on days 1-5, one hour following the administration of TMZ. In absence of contraindications (known allergies), **systematic treatment with oral cefixime 8 mg/kg once a day (maximum daily dose 400 mg) is recommended and will be started 2 days before chemotherapy until day 7** (see Appendix 11 for cefixime management in The Netherlands).

Temozolomide: will be given according to the randomization: The starting dose of TMZ will be 125 mg/m²/day. The dose of TMZ will be escalated to 150 mg/m²/day at cycle 2 for patients who do not experience ≥ grade 3 toxicity of any kind. The dose of TMZ should be rounded to the nearest 5 mg. TMZ will be given orally, on an empty stomach, prior to vincristine and irinotecan, on days 1-5 repeated every 3-weeks. If the patient vomits within 20 minutes after TMZ, the dose will be re-administered. The capsules must be swallowed whole with a glass of water. For young children and patients who have difficulty swallowing capsules, the full daily dose of TMZ capsules should be placed

in 10-30 ml fruit juice or compote and administered after the capsules have been allowed to soften for 15-20 minutes or according to normal local practice for patients in the United Kingdom (see Appendix 12).

Treatment will continue until disease progression, unacceptable toxicity or the patient's desire to discontinue therapy. Local treatment is allowed after 2 cycles.

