- Partial Response (PR): At least a 30% decrease in the sum of the longest diameters of all target lesions, taking as reference the disease measurement done to confirm measurable disease at study enrolment.
- Progressive Disease (PD): At least a 20% increase in the sum of the longest diameters of all target lesions, taking as reference the smallest disease measurement recorded since the start of treatment. In addition to the relative increase of at least 20% the sum must also demonstrate an absolute increase of at least 5mm (*Note: the appearance of one or more new lesions is also considered progression*)

- Stable Disease (SD): Neither sufficient shrinkage to qualify for PR nor sufficient increase to qualify for PD taking as reference the smallest disease measurement since the treatment started.

NOTES:

- *Lymph nodes* identified as target lesions should always have the actual short axis measurement recorded (measured in the same anatomical plane as the baseline examination) even if the nodes regress to below 10mm on study. This means that when lymph nodes are included as target lesions, the "sum" of lesions may not be zero even if complete response criteria are met, since a normal lymph node is defined as having a short axis of <10 mm.
- *When lesions 'fragment'*, the individual lesion diameters should be added together to calculate the target lesion sum. Similarly, as lesions coalesce, a plane between them may be maintained that would aid in obtaining maximal diameter measurements of each individual lesion. If the lesions have truly coalesced such that they are no longer separable, the vector of the longest diameter in this instance should be the maximal longest diameter for the 'merged lesion'.

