11.1.2. Overall Tumour Response (=Primary tumour and Metastatic lesions)

The overall response assessment takes into account the response in the primary tumour and metastases according to the criteria in the table below. The overall response assessment is shown in the last column, and depends on the assessments of the response in the primary tumour, target and non-target lesions, and the development of new lesions.

Primary Tumour	Target Lesions	Non-Target Lesions	New Lesions	Overall Response
CR	CR	CR	No	CR
CR	CR	Incomplete response/SD	No	PR
PR	PR	Non-PD	No	PR
Minor PR	Non-PD	Non-PD	No	Minor PR
SD	SD	Non-PD	No	SD
Any	PD	Any	Yes or No	PD
Any	Any	PD	Yes or No	PD
Any	Any	Any	Yes	PD

If a patient has not tumor evaluation due to clinical disease progression, it will be classified as a progressive disease.

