11.1.3. Objective tumour response and progression

Primary efficacy endpoint

The primary efficacy endpoint is defined as the proportion of patients who had a documented complete or partial tumour response occurring after the first 2 cycles of treatment which must be confirmed by a follow-up objective tumour assessment obtained within 4-5 weeks after the initial documentation.

Secondary endpoints

Secondary efficacy endpoints are defined as follows:

- The best overall response is the best response recorded from the start of the treatment until disease progression/recurrence (taking as reference for PD the smallest measurements recorded since the treatment started) over the whole treatment duration. It must be confirmed by a follow-up objective tumour assessment obtained within 4-5 weeks after the initial documentation.
- Duration of tumour response: the time from first documentation of objective tumour response to the first objective or clinical documentation of progression
- Time to treatment failure: the time from the date of first treatment administration to the first documentation of tumour progression, discontinuation of study treatment before one year, or death, whichever occurs first
- Progression-free survival (PFS): the time from the date of first treatment administration to the date of first objective or clinical documentation of tumour progression or death due to any cause
- Overall survival (OS): the time from the date of first treatment administration to date of death

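### Section 7.4 shields only an undefined main target lesion from concurrent palliative radiotherapy, so an irradiated secondary target can complete a partial response at the 2-cycle scan

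*Protocol*

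**What the plan says.** Two radiotherapy rules stand in the same list in section 7.4.

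- Prior radiotherapy: more than 3 weeks must have passed since "prior radiation therapy to the site of any progressive lesion that will be identified as a target lesion to measure tumor response".
- Concurrent radiotherapy: "Concurrent palliative radiation therapy to sites allowed except for the main measurable target lesion".

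Section 11.1.1 then sets out how metastatic disease is measured: "The investigator will identify up to 5 target lesions total and up to 2 per organ to be followed for response". No lesion is ranked above the others. "The sum of the longest diameters of all target lesions will be calculated and reported as the measurable metastatic disease measurement", and PR on that component is "At least a 30% decrease in the sum of the longest diameters of all target lesions". The primary is measured by volume and needs a reduction of at least 65% for PR.

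Section 11.1.2 combines the parts: "The overall response assessment takes into account the response in the primary tumour and metastases according to the criteria in the table below". The row that yields PR from a primary in PR also requires PR of the target lesions, no progression of non-target lesions and no new lesion.

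The primary endpoint (11.1.3) is complete or partial response after the first 2 cycles, which "must be confirmed by a follow-up objective tumour assessment obtained within 4-5 weeks after the initial documentation". On timing, section 9.1 says: "Local treatment is allowed after 2 cycles". Section 7.5 excludes concomitant anticancer treatment in general terms.

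**The concern.** The prior-radiotherapy rule recognises that recent irradiation of any target lesion confounds response. The concurrent rule protects one lesion only and does not say which. No text in the protocol removes a target lesion irradiated during cycles 1 and 2 from the diameter sum or makes it non-evaluable. A site that follows the protocol exactly can therefore irradiate a metastatic or nodal target, measure its shrinkage at the 2-cycle scan and count it towards PR.

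The primary endpoint is meant to show chemotherapy activity, and the VIT response count guides whether VIT goes forward. A PR reached only because a target was irradiated is a misclassified response. Section 13.9 would not catch it. The items that sites must keep up to date for central review are examinations, cycle dates, and the date and reason of discontinuation. Radiotherapy site and date are not among them, and the reviewers have no rule to apply.

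**Working it through.** The protocol gives no figure for this point, so there is nothing to reproduce. The check applies its own thresholds to an example. All lesion sizes and shrinkages below are assumptions.

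**Thresholds from 11.1.1 and 11.1.2.** Primary PR: volume reduction of at least 65%. Target-lesion PR: fall in the sum of at least 30%. The PR row needs both.

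**Example.**

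1. Primary: all three diameters fall from 50 to 34 mm. Volume change = 1 − (34/50)³ = 1 − 0.314 = 0.686, a 69% reduction, so PR.
2. Metastatic targets at baseline: 35 + 25 = 60 mm. PR needs a sum of at most 0.70 × 60 = 42 mm.
3. No radiotherapy, both targets fall 20%: 28 + 20 = 48 mm, a 20% fall, stable disease. The PR row is not met.
4. The 35 mm lesion is irradiated and halves, the other falls 20%: 17.5 + 20 = 37.5 mm, a 37.5% fall, PR. The row is met.
5. Smallest shrinkage that is enough: 42 − 20 = 22 mm, so the irradiated lesion must fall by 1 − 22/35 = 37%.

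**How far the example can move.** With the same two lesions:

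- Irradiate the 25 mm lesion instead, with a 40% fall, and let the other fall 20%: 28 + 15 = 43 mm, a 28.3% fall, stable disease.
- Halve the 35 mm lesion with the other unchanged: 17.5 + 25 = 42.5 mm, a 29.2% fall, stable disease.

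For equal-sized targets where irradiated lesions fall 50% and the others 20%, the sum falls 35% with 1 of 2 irradiated, 30% with 1 of 3 and 32% with 2 of 5 (all PR). It falls 27.5% with 1 of 4 and 26% with 1 of 5 (stable disease).

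**General condition.** If irradiated lesions fall by h and the others by d, their share s of the baseline sum must be at least s = (0.30 − d)/(h − d).

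| h | d = 0 | d = 0.20 |
|---|---|---|
| 0.40 | 75% | 50% |
| 0.50 | 60% | 33% |
| 0.60 | 50% | 25% |

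**Sensitivity of the decision rule (illustration only).** Section 12.1 (revised design) has p0 = 0.35 and calls VIT sufficiently active at 22 or more responders of 47. At a true rate of 0.35, suppose k responses are false. The lower figure counts k given patients as responders whatever the drug does, P(Bin(47 − k, 0.35) ≥ 22 − k). The upper figure always converts non-responders, P(Bin(47, 0.35) ≥ 22 − k).

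| k | lower | upper |
|---|---|---|
| 0 | 0.063 | 0.063 |
| 1 | 0.089 | 0.109 |
| 2 | 0.121 | 0.175 |

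The documents give no basis for choosing k.

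**The case against.** **Other sections seem to bar early radiotherapy.** The general exclusion in 7.5 and the timing statement in 9.1 suggest an intent to keep the first 2 cycles free of local treatment. Neither withdraws the specific permission in 7.4; read as a bar, 7.5 would leave that line without effect.

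**The main lesion can be understood.** In a trial built on volumetric response, it may naturally be the lesion measured by volume, usually the primary. That is plausible, and it would protect the harder component. It still leaves every metastatic and nodal target open.

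**The route is narrow.** This stands. It needs a primary already in PR, targets short of a 30% fall, palliative radiotherapy to one of them during cycles 1 and 2, and enough shrinkage by the scan. Bone lesions without a measurable soft-tissue component are not targets, so irradiating them cannot affect the sum. Section 5.1 reports that relapse is locoregional in 76% and isolated metastatic in 15%. Those figures concern disease that was localised at first, but they suggest that a primary with metastatic targets is not the typical case.

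**Balance and the cut-off.** The VI arm has the same permission, and section 12.2 treats the cut-off as a guideline read alongside the VI rate. Balance does not remove inflation against a fixed cut-off, but this does soften the consequence.

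**A stronger reading is tempting.** A reader might infer that radiotherapy alone can create a PR in a patient with metastases only. The documents do not support that as a finding. It requires judging such a patient by diameter sum, while section 5.1 makes volumetric response the main criterion and 7.4 requires lesions measurable in 3 dimensions. How a patient without a measurable primary is judged is a separate point.

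**Conclusion.** The point holds as an inconsistency within section 7.4 that reaches the primary endpoint. As written, the protocol allows an irradiated metastatic or nodal target to complete an overall PR in a patient whose primary is already in volumetric PR. Radiotherapy to such a target cannot create that PR alone, because the primary must itself shrink by at least 65% in volume, so some drug activity is present. New lesions still count as progression.

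The size is limited and cannot be estimated from the documents. How often targets would be irradiated is not stated and is probably low, and the shrinkage figures are assumed. A reader might infer from the sensitivity table that the decision rule exceeds its 0.10 error rate. The documents do not support that: the number of false responses is hypothetical, and with one of them the result lies on either side of 0.10 depending on the model. The case for change is that the gap is plain in the text and cheap to close.

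**What to change.** 1. Reword 7.4 to match the prior-radiotherapy rule: *Concurrent palliative radiotherapy is allowed except to the primary tumour or any lesion chosen as a target lesion.*
2. State in 11.1 that a primary or target lesion irradiated before the 2-cycle assessment cannot contribute to complete or partial response but still counts for progression. Response is judged on the unirradiated measurable lesions, and a patient with none left is a non-responder.
3. Cover the confirmatory scan. Section 9.1 allows local treatment after 2 cycles and confirmation follows 4 to 5 weeks after first documentation, so radiotherapy can fall between the two. Confirmation should then also rest on the unirradiated lesions, or the response should be reported as confirmed under local treatment.
4. Add radiotherapy site and date to the items in 13.9, so that central reviewers can apply points 2 and 3.

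The cost is wording in three sections and two data items for the reviewers. Palliative radiotherapy to non-target sites stays available, and a target that must be irradiated can still be treated. The downside is that a few responses in irradiated patients are lost, a small downward bias of unknown size.
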